Laboratory assessments – Local labs	X a				X b				Hematology, biochemistry panels and coagulation: a. To be performed at screening within 7 days of Cycle 1 D1 after patient has discontinued AI. b. At each visit during the treatment period, at EOT, and as clinically indicated.  Lipids assessments on Visit 1, Visit 3, Visit 4, and as clinically indicated.

Procedure	Screening Period	Treatment Period [5 years – C1-C65]					EOT	Follow-up Period	Notes
		1	2	3	4-10 Q12 weeks	11-16 Q24 weeks			
Patient Visit #	0	1	2	3	4-10 Q12 weeks	11-16 Q24 weeks	17	≥18	
Patient Cycle Visit #	Baseline	C1 D1	C2 D1	C4 D1	C7, C10, C13, C16, C19, C22, C25 D1	C28, C34, C40, C46, C52, C58 D1	D30 after last IMP dose	Q12 months after last IMP dose	
Time Window (day)	Up to 28 days before randomization	±3	±3	±7	±7	±7	±7	±45	
Bone mineral densitometry ) / Dual-energy X-ray absorptiometry (DXA)	X a				X b				a. Screening: to be done if not already done in the past 12 months prior to randomization. b. Post baseline: every 2 years from randomization (+/-1 month) until end of follow -up period Other quantitative methods giving similar T-score values, including ultrasound bone densitometry and QCT (quantitative computerized tomodensitometry) are also accepted.
Bone Turnover Markers (CTX, P1NP) – Local labs	X a				X b				a. Screening: to be done if not already done in the past 12 months prior to randomization. b. During the treatment period: every 2 years from randomization (+/-1 month)
12-lead ECG	X						X		Screening (after patient has discontinued AI), EOT and as clinically indicated

Procedure	Screening Period	Treatment Period [5 years – C1-C65]					EOT	Follow-up Period	Notes
		0	1	2	3	4-10 Q12 weeks			
Patient Visit #	Baseline	C1 D1	C2 D1	C4 D1	C7, C10, C13, C16, C19, C22, C25 D1	C28, C34, C40, C46, C52, C58 D1	D30 after last IMP dose	Q12 months after last IMP dose	
Patient Cycle Visit #	Up to 28 days before randomization	±3	±3	±7	±7	±7	±7	±45	
Time Window (day)	X								Eligibility criteria data collection and central confirmation of ER and PgR biomarkers to be completed prior to IRT randomization call
Randomization									
Study Treatment Administration:									
IMP dispensation call		X		X	X	X a			a. Visit 16 (C58): IMP dispensation from C58 to C65, ie, 32 weeks
amcenestrant + tamoxifen-matching placebo		Once daily ↔							
tamoxifen + amcenestrant-matching placebo		Once daily ↔							

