Time Window (day)		X a	X a				X b		Refer to Section 8.6.2 for details a. Pre-dose b. Collected at EOT for patients who discontinued treatment due to disease recurrence
(Optional) Blood Samples for Future Research									

All study visits performed during treatment period and follow-up period are conducted on-site (in participants without disease recurrence). On-site visits could be substituted by remote visits in specific circumstances.

**Screening:** Routine baseline tests performed prior to ICF signature do not need to be repeated as long as they are within the screening defined timeframe. Informed consent should be signed before any study specific procedures. It can be signed more than 28 days prior to randomization. Screening time indicates in which timeframe exams used to support eligibility have to be done prior to randomization.

**Randomization:** To take place once the consented patient has completed all the necessary screening procedures and is deemed eligible for study entry by the Investigator or designee. All eligible patients must be randomized using IRT. Every effort should be made to start treatment within 3 working days of randomization.

**Treatment period:** A cycle is defined as a 28-day period. Men and pre/perimenopausal women will receive GnRH analog on D1 of the cycle.

**Physical examination/ signs and symptoms evaluation:** At a minimum, assessments of the cardiovascular system, pulmonary system, gastrointestinal system (including palpation of liver and spleen), examination of the skin, and breast exam (palpation of breast/chest wall, axillae, supra- and infraclavicular regions). Symptom-directed physical examinations should be performed at screening and at each subsequent visit.

**Cycle 1 D1** refers to the day the patient receives the initial dose of IMP. Repeated evaluation of body weight, signs and symptoms, physical examination and laboratory tests is not necessary if performed within 7 days prior to 1st IMP administration. If evaluation performed during screening is abnormal, repeated evaluation is recommended within 2 days prior to 1st IMP administration.

**End of treatment (EOT):** should be performed 30 days (±7 days) after the last IMP and prior to the initiation of any new anti-cancer therapy, whichever comes first.

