#### **5.3.1 Sun protection**

A phototoxicity risk for amcnestrant was identified based on the absorption spectrum of the compound in *in vitro* and *in vivo* preclinical studies. Within the amcnestrant development program which includes the below recommendations, cumulatively Grade 1 sunburns were observed only in 2 patients out of an approximately 700 participants exposed so far to amcnestrant doses (from 20 to 1200 mg).

Participants should avoid direct exposure to natural or artificial sunlight during study treatment and for at least 5 days after last amcnestrant/amcnestrant-matching placebo dose. It is recommended to advise to wear protective clothing, lip balm, and broad-spectrum sunscreen with a high sun protection factor (eg,  $\geq 30$ ) to cover UVA and UVB light exposure when outdoors with frequent re-application as necessary.

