#### 9.2.1 General considerations

The baseline value is defined as the last available value before randomization, unless otherwise specified.

Unless otherwise specified, analyses will be performed by intervention group (and overall for baseline and demographics characteristics).

The observation period will be divided into 3 segments:

- The **pre-treatment period** is defined as the period up to first IMP administration.

- The **on-treatment period** (ie, treatment-emergent (TE) period) is defined as the period from the first IMP administration to the last IMP administration + 30 days.
- The **post-treatment period** is defined as the period from the end of the on-treatment period.

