### **9.2.5.2 Laboratory variables, vital signs and electrocardiograms (ECGs)**

#### **Analyses according to PCSA and NCI grading**

For laboratory variables, analyses according to NCI grading will be made based on NCI-CTCAE version 5.0. In addition, for laboratory variables for which NCI-CTCAE scale is not applicable, vital signs and ECG variables, PCSA analyses will be performed based on the PCSA list currently in effect at Sanofi at the time of the database lock.

Analyses according to PCSA and NCI grading will be performed based on the worst value during the treatment-emergent period, using all measurements (either local or central, either scheduled, nonscheduled or repeated).

For laboratory variables, vital signs and ECG variables, the incidence of participants with at least one PCSA during the treatment-emergent period will be summarized regardless of the baseline level and according to the following baseline status categories:

- Normal/missing
- Abnormal according to PCSA criterion or criteria

For laboratory variables graded by NCI-CTCAE.

- The number (%) of participants with abnormal laboratory tests at baseline will be presented by grade.
- The number (%) of participants with abnormal laboratory tests during the treatment-emergent period will be summarized by grade. When appropriate, the number (%) of participants with abnormality of any grade and with Grade 3-4 abnormalities will be provided.

For ECG, the incidence of participants with at least one abnormal ECG during the treatment-emergent period will be summarized regardless of the baseline level and according to the following baseline status categories:

- Normal/missing
- Abnormal

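### No ECG is scheduled during dosing, so the treatment-emergent ECG analysis rests on post-dosing EOT tracings and clinically indicated ones

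*Combined protocol and SAP*

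**What the plan says.** - **ECG timing.** The 12-lead ECG row in Section 1.3 is marked at screening and EOT only, with the note "Screening (after patient has discontinued AI), EOT and as clinically indicated". Section 8.2.2 refers ECG timing back to this schedule and adds no visit.
- **EOT timing.** The column is headed "D30 after last IMP dose", and the accompanying note says the visit "should be performed 30 days (±7 days) after the last IMP and prior to the initiation of any new anti-cancer therapy, whichever comes first".
- **Treatment-emergent period.** Section 9.2.1 says the on-treatment period "is defined as the period from the first IMP administration to the last IMP administration + 30 days".
- **Planned analysis.** Section 9.2.5.2 states: "For ECG, the incidence of participants with at least one abnormal ECG during the treatment-emergent period will be summarized". It also plans PCSA incidence for ECG variables, taking the worst value in the same period, "using all measurements (either local or central, either scheduled, nonscheduled or repeated".
- **Analysis dates.** Table 7 expects the two interim cut-offs at 28 and 48 months and the final IBCFS cut-off at 60 months after the first randomization. The planned treatment duration is 5 years (C1 to C65).

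**The concern.** Section 9.2.5.2 treats ECGs like laboratory values: the worst post-baseline result in the treatment-emergent period, by arm and by baseline status. Laboratory tests are drawn at every treatment visit, so that method has dosing-period data to work on. For ECGs it has none that are scheduled.

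What the method would pick up is of two kinds. One is a tracing taken after dosing has ended. The other is a tracing ordered because something prompted it, which is selective and may differ between arms for reasons unrelated to cardiac effect. A reader who sees a treatment-emergent ECG table for a drug given for 5 years will naturally take it to describe ECGs during treatment.

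Adverse event reporting does not fill the gap. Under Section 8.2.2 an ECG abnormality becomes an adverse event only if it is symptomatic, needs corrective treatment, leads to discontinuation or dose modification, or is serious. An asymptomatic interval change would therefore appear only in the ECG table, if it was recorded at all. Tracings not taken during dosing cannot be recovered later.

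**Working it through.** The plan states no figure for this point, so there is none to reproduce. The check is a count and calendar arithmetic.

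1. **Scheduled ECGs during dosing.** Treatment-period visits in Section 1.3: C1, C2 and C4 (3), C7 to C25 (7), C28 to C58 (6). Total 3 + 7 + 6 = 16. ECGs scheduled at these visits: 0, over 65 × 28 = 1820 days.

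2. **EOT window against the treatment-emergent cut.** The window is 30 − 7 = day 23 to 30 + 7 = day 37 after the last dose, which is 15 calendar days. The treatment-emergent period ends at day 30.
   - Days 23 to 30: 8 days, counted.
   - Days 31 to 37: 7 days, not counted although the visit is compliant.
   - 7/15 = 47% of window *days*. This is not a share of tracings, because the documents say nothing about how visits spread over the window.

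3. **When a completer reaches EOT.** With C1D1 as the first dosing day, the last of 1820 dosing days is 1819 days later.
   - Earliest in-window EOT: 1819 + 23 = 1842 days after C1D1; 1842/30.4375 = 60.5 months.
   - Latest: 1819 + 37 = 1856 days; 1856/30.4375 = 61.0 months.
   - Final cut-off: 60 × 30.4375 = 1826 days after the first randomization.

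   Even the first participant randomized would reach an in-window EOT after the cut-off. Reading the duration as 5 calendar years (about 1826 days) makes EOT about 6 days later still. At the 28- and 48-month interims no completer exists.

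4. **How firm step 3 is.**
   - EOT can be brought forward before new anti-cancer therapy. If it fell on the day after the last dose (day 1820), only participants first dosed within about 1826 − 1820 = 6 days of the start could contribute by the cut-off.
   - Suppose the cut-off slipped to 63 months (63 × 30.4375 = 1918 days). In-window completers would then be those first dosed within (1918 − 1842)/30.4375 = 2.5 months of the start. That is fewer than the 5% that Table 12 expects by month 3 (0.05 × 3738 = about 187). A longer slip would admit more.

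**The case against.** **The target day agrees with the definition.** EOT is set at day 30, and the treatment-emergent period runs through day 30. The plan openly includes 30 days after the last dose and admits unscheduled tracings, and it nowhere calls the table a comparison during dosing. This stands. Nobody should infer that the table is empty: EOT ECGs on days 23 to 30, EOT ECGs brought forward before new therapy, and clinically indicated ECGs all count. It does not supply a scheduled tracing during dosing.

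**Sparse ECGs may be proportionate.** Table 1 lists no cardiac or ECG risk for either drug, no adverse event of special interest is cardiac, and ECG is not named in the safety endpoint. The Investigator's Brochure, which is not available here, may settle the question. This limits the importance of the point. It does not explain why Section 9.2.5.2 plans a treatment-emergent analysis on data that the schedule does not produce.

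**Other text might cure it.** Section 7.1.2 asks, where possible, for the procedures of the last dosing day after discontinuation, but the schedule has no such visit and places the ECG at EOT. Section 9.2 leaves technical detail to a SAP. The supplied text shows no further rule for EOT ECGs, and no analysis rule can create ECGs that were not taken.

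**Two stronger readings are not supported.**
- A reader might infer from 7 of 15 days that about half of the EOT tracings are lost. That assumes visits spread evenly over the window and ignores EOT visits brought forward; the true share is unknown.
- A reader might infer that the EOT ECG compares a cleared drug with a retained one. For amcenestrant, the only hint is sun protection "for at least 5 days after last amcnestrant/amcnestrant-matching placebo dose", a minimum skin precaution and not a statement about clearance; no half-life is given. For tamoxifen, the contraception rules in Section 10.4 imply different half-lives: (160 − 90)/5 = 14 days from the male rule, and about 3 months/5 = 18 days from the female rule. The documents cannot carry that argument.

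**Conclusion.** The point holds. There are 0 scheduled ECGs at 16 dosing-period visits, and the single scheduled post-baseline ECG comes after dosing has ended. Part of its permitted window (7 of 15 days) lies outside the period in which it would be analysed, with an unknown effect on participant numbers. At the final analysis, and more so at a positive second interim, scheduled post-baseline ECGs would come almost only from participants who stopped early.

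The first two statements rest on the text alone. The last assumes that the cut-off falls near the planned 60 months and that EOT is held within its window; it weakens if the cut-off slips well beyond that.

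The consequence is limited but real: the table cannot describe ECG effects during dosing, in either direction. It does not touch the primary endpoint, and the plan does not itself claim to show absence of an ECG effect. It is worth correcting because the remedy is cheap and the missing data cannot be obtained afterwards.

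**What to change.** Reconcile Sections 1.3, 9.2.1 and 9.2.5.2.

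**Preferred.** Move the one scheduled post-baseline ECG from EOT to an existing on-treatment site visit chosen by the sponsor. The number of ECGs per participant is unchanged and no visit is added. The table would then hold a scheduled tracing during dosing from participants still on treatment at that visit, available at the final analysis. A single tracing would still not describe 5 years of treatment.

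*Cost:* loss of the exit tracing, and a protocol amendment, which under Section 10.1.2 needs ethics approval and, if substantial, health-authority approval.

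**If the ECG stays at EOT.**
- Classify the EOT ECG by visit, so that a compliant tracing on days 31 to 37 is not dropped by date.
- Report it as a post-dosing ECG, separately from ECGs taken during dosing.
- State in Section 9.2.5.2 that the table does not describe ECG effects during dosing.

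*Cost:* a few sentences of analysis text and no change at sites. Simply extending the treatment-emergent period to day 37 is not a substitute: it would put more post-dosing tracings under a treatment-emergent label and would also reclassify other EOT safety data, such as laboratory results.

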## 2 INTRODUCTION

Both endogenous and exogenous steroid hormones such as estrogen and progesterone are known to contribute to the pathogenesis of breast cancer. Clinical treatment decisions of breast cancer are commonly driven by tumoral expression of hormone receptors (HRs), namely ER and progesterone receptors (PgR), as well as expression of HER2. While breast cancer can be subdivided by numerous systems, the most clinically relevant subtypes are HR-positive, HER2-positive (HER2+), and triple-negative breast cancer. About 75% of breast cancers express estrogen ER $\alpha$  which is a hormone receptor that regulates gene transcription (5).

As estrogens have a major impact in breast cancer development and progression, endocrine treatment (ET) is an increasingly and systematically used treatment option as adjuvant (after surgery) or neoadjuvant (before surgery) therapy (6, 7, 8). The current ETs that are used in the adjuvant setting are tamoxifen, a selective ER modulator (SERM) that acts by blocking the ER, and the AIs (letrozole, anastrozole, and exemestane), which reduce estrogen levels by inhibiting the peripheral synthesis of estrogen (9, 10).

Amcnestrant is a potent, orally bioavailable, and selective ER $\alpha$  inhibitor that belongs to the SERD class of compounds. SERDs have the potential to block endocrine-dependent and endocrine-independent ER $\alpha$  signalling by ablation of ER $\alpha$  and have been recognized to offer a therapeutic approach to ER $\alpha$  positive breast cancer in both early-stage breast cancer and advanced breast cancer. Amcnestrant antagonizes the binding of estradiol to ER but also promotes the transition of ER $\alpha$  to an inactive conformation that leads to up to 98% receptor degradation at sub-nanomolar concentrations in cellular assays.

These dual properties of amcnestrant translate in a deeper inhibition of ER $\alpha$  pathways and a more effective anti-proliferative activity in ER $\alpha$ -dependent breast cancer cell lines driven by mutant or wild-type ER $\alpha$  compared to other ER $\alpha$  inhibitors.

Amcnestrant has the potential to provide effective and well-tolerated therapy for patients with early and advanced breast cancer with a convenient route of administration, oral (PO) versus intramuscular (IM), better bioavailability, and long-term maintenance of ER receptor blockade combined with a strong antitumor activity as compared to fulvestrant. A detailed description of the chemistry, pharmacology, pharmacokinetics, preliminary efficacy, and safety of amcnestrant is provided in the IB.

Fulvestrant is the only currently approved SERD for HR+, HER2- metastatic breast cancer. Fulvestrant is approved for the treatment of patients with advanced breast cancer (either as monotherapy or in combination with targeted anticancer drugs) but it is not indicated as adjuvant endocrine therapy for patients with early-stage breast cancer. Fulvestrant has shown clinical benefit in the treatment of breast cancer patients who have progressed during endocrine therapies such as tamoxifen or AIs. However, fulvestrant must be administered as a monthly IM injection of a 500 mg dose to each gluteus maximus. Although fulvestrant has served as an important proof of concept for the SERD approach, this therapy is limited by its poor pharmaceutical properties which necessitate intramuscular administration and limits the applied dose, exposure, and optimal receptor engagement.

## 2.1 STUDY RATIONALE

### 2.1.1 Study rationale and purpose

The purpose of the proposed study is to demonstrate the superiority of amcnestrant *versus* tamoxifen with regards to IBCFS in patients with HR+ early breast cancer who have discontinued aromatase inhibitor as adjuvant treatment due to treatment-related toxicities. For this population, there are currently limited treatment options after AI discontinuation, including switching to another AI which may have similar side effects, or switching to tamoxifen. This paucity of effective and tolerable options may contribute to early discontinuation of adjuvant endocrine therapy. Poor adherence has been shown to be associated with worse outcomes (11, 12). It is estimated that about 30% of the patients treated with aromatase inhibitor discontinue their adjuvant therapy and that 22% discontinue during the first year (1, 11). The primary endpoint of this study will be IBCFS defined as occurrence of first recurrence of the disease: ipsilateral or regional invasive, distant recurrence, contralateral invasive breast cancer and death.

### 2.1.2 Rationale for dose and regimen selection

#### 2.1.2.1 AMEERA-1 trial

The Phase 1/2 first-in-human (FIH) dose escalation and expansion AMEERA-1 (TED14856) study with amcnestrant single agent, has been designed for women with heavily pretreated, postmenopausal advanced or metastatic HR+/HER2-, breast cancer.

A strong pharmacokinetic/pharmacodynamic relationship was established between amcnestrant plasma concentrations and associated F-FES PET percent occupancy of the ER. Overall mean occupancy per patient was 95.6% and 94.0% with amcnestrant 400 mg QD and 150-600 mg QD, respectively. The recommended dose of amcnestrant was established at 400 mg once daily when used as monotherapy for the treatment of advanced breast cancer.

In AMEERA-1, the antitumor activity of amcnestrant as monotherapy was assessed in 59 evaluable patients (treated from 150 to 600 mg QD) as well as in a subset of patients naïve from targeted therapies and fulvestrant. In the overall study population, the best overall responses (BOR) based on RECIST 1.1 criteria were 5 confirmed partial responses (PR; 8.5%), 24 stable disease (SD; 40.7%) and 30 progressive disease (PD; 50.8%). The antitumor activity observed in this population of heavily pretreated patients showed durable control of the disease with a high rate of clinical benefit [CBR (CR + PR + SD  $\geq$ 24 weeks) = 33.9%] (13).

Amcnestrant demonstrates a favorable safety profile. Limited treatment-emergent adverse events (TEAEs) related to amcnestrant as monotherapy were observed on AMEERA-1, all Grade 1 and 2, the most frequent being: hot flush, arthralgia, and constipation.

### **2.1.2.2 Antitumor activity of amcnestrant compared to fulvestrant**

A comparison of the AMEERA-1 results with those of fulvestrant in the medical literature was undertaken in order to place the amcnestrant data in the context of historical data. A total of 4 comparative studies were selected wherein fulvestrant was given as monotherapy and in which study eligibility criteria excluded patients with prior targeted therapies (mTOR and CDK 4/6 inhibitors) and prior use of fulvestrant (14, 15, 16, 17). The objective response rate (ORR) and the CBR were indirectly compared with the recommended 500 mg dose of fulvestrant monotherapy in the second or third line setting among postmenopausal women with advanced/metastatic ER+/HER2- breast cancer and whose tumor responses were confirmed as per RECIST v1.1 in populations with measurable disease. The PALOMA-3 (13) and FAKTION (14) studies recruited women who had received up to 3 prior lines of endocrine therapy and the SOLAR-1 (15) and SANDPIPER (16) studies with up to 2 prior lines. The PALOMA-3 study excluded women who had received prior fulvestrant and CDK4/6, PI3K, and/or mTOR inhibitors. The FAKTION, SOLAR-1 and SANDPIPER studies excluded women who had received prior fulvestrant and PI3K inhibitors, and the SOLAR-1 and SANDPIPER studies also excluded women who had received prior mTOR inhibitors. All four comparator studies investigated less heavily pre-treated patients than in AMEERA-1. In these studies, the fulvestrant monotherapy ORR ranged from 10.9–16.2% and CBR ranged from 36.0-44.1% (18, 19, 20, 21). Meanwhile, the ORR and CBR in AMEERA-1 study in a similar subset population (14 patients who had not received prior therapy with fulvestrant, an mTOR inhibitor, or a CDK 4/6 inhibitor) compared favorably to these historical data with ORR of 21.4% and CBR of 64.3%.

Given the demonstrated antitumor activity and safety of amcnestrant in the treatment of advanced breast cancer, there is interest in whether amcnestrant may also offer an effective and safe treatment option in the adjuvant setting. In order to address the early-stage breast cancer population, short-term preoperative studies are considered as a validated strategy to provide rapid and cost-efficient proof-of-concept for novel treatment approaches by assessing the direct effects of the study treatment on the tumor tissue (22, 23). Detailed studies in the neoadjuvant setting in prospective randomized clinical trials have demonstrated the utility and validity of changes in Ki67 as a predictor of benefit from treatment and of long-term outcome (24, 25). For example, in the preoperative IMPACT study, suppression of Ki67 at 2 weeks was greater with anastrozole than with either tamoxifen or the combination of anastrozole plus tamoxifen, and this was correlated with recurrence-free survival (26, 27).

